5.2.2 Timing of Dose Administration

Trial treatment should be administered on Day 1 of each cycle after all procedures/assessments have been completed as detailed on the Study Calendar (Section 6.0). Trial treatment may be administered up to 3 days before or after the scheduled Day 1 of each cycle due to administrative reasons.

All trial treatments will be administered on an outpatient basis.

Pembrolizumab 200 mg will be administered as a 30 minute IV infusion every 3 weeks. Sites should make every effort to target infusion timing to be as close to 30 minutes as possible. However, given the variability of infusion pumps from site to site, a window of -5 minutes and +10 minutes is permitted (i.e., infusion time is 30 minutes: -5 min/+10 min).

5.3 Treatment

The dose escalation portion of the trial will determine the MTD. Once the dose escalation portion is complete, patients will enroll sequentially (see Statistical Analysis Plan section for further details) into one of two expansion cohorts as noted below. Enrollment into Expansion Cohorts A and B are pre-planned in regards to sequence and timing. Arm A (lead in trametinib) will open first to dose escalation and will accrue 3 patients. Once 3 patients are accrued for Arm A, Arm B will open and accrue 3 patients.

Expansion Cohort (Arm)	Regimen	Number of patients
A	Lead in trametinib for 1 cycle (Q3W) followed by intercalated Trametinib and Pembrolizumab.	12
В	Lead in pembrolizumab for 1 cycle (Q3W) followed by intercalated Trametinib and Pembrolizumab.	12

5.4 Definition of Dose Limiting Toxicities

All toxicities will be graded using National Cancer Institute (NCI) CTCAE Version 4.0. The occurrence of any of the following toxicities during the first two cycles (i.e. after completion of the lead in cycle and the first cycle where both pembrolizumab and trametinib are administered) will be considered a DLT, if judged by the Investigator to be possibly, probably or definitely related to study drug administration. The goal of the dose escalation portion of the study is to assess the safety of the combination after pembrolizumab or trametinib lead in, therefore, patients must have completed the lead in phase and also have received both trametinib and pembrolizumab concurrently to be evaluable for a DLT.

A DLT evaluable subject is defined as a subject who receives treatment for the 6 week dose-limiting toxicity (DLT) observation period and who receives at least 80% of all planned treatments. A subject who does not receive at least 80% of planned treatment due to AEs that are unrelated to study treatment will not be considered evaluable for DLTs and may be replaced as

needed during dose escalation or dose confirmation. More than 3 or 6 subjects may be enrolled to a given dose level if needed to replace subjects who are not evaluable for DLT or to ensure a thorough evaluation of a given dose level during the dose escalation part of the study. An event will be considered a dose-limiting toxicity (DLT) if it occurs during the first two cycles of treatment (first 6 weeks after initiating treatment) and meets at least one of the following criteria:

- Clinically significant hematologic toxicity (e.g. grade 4 neutropenia lasting more than 7 days or accompanied by neutropenic fever, or Grade 4 thrombocytopenia of any duration)
- Clinically significant Grade ≥3 non-hematologic toxicity that has not been previously identified for either pembrolizumab or dabrafenib/trametinib and cannot be controlled with routine supportive measures (e.g. anti-emetics)
- Clinically significant Grade ≥3 non-hematologic toxicities that are known to occur with either pembrolizumab or trametinib but that cannot be controlled using the recommended product-specific supportive measures (e.g. steroids for pembrolizumab -related immune toxicities)
- Drug-related toxicity, regardless of CTCAE grade, that results in an interruption of any component of study therapy during Cycle 1 for more than 21 consecutive days and cannot be controlled within 2 weeks from its onset
- Any other Grade 2 or greater non-hematological toxicity that in the judgment of the investigator and Sponsor Investigator is dose limiting, with the exception of mild or moderate immune -mediated adverse reactions or symptomatic endocrinopathy attributable to pembrolizumab
- For Liver Function Tests
 - ALT or AST $\geq 8x$ ULN
 - ALT or AST \geq 5x ULN but \leq 8x ULN persists for \geq 2 weeks
 - ALT or AST ≥3x ULN if associated with the appearance or worsening of symptoms of hepatitis or hypersensitivity such as fatigue, nausea, vomiting, right upper quadrant pain or tenderness, pyrexia, rash or eosinophilia.

The following will NOT be considered a DLT for the purposes of this protocol:

• Clinically insignificant laboratory values of any grade (i.e. asymptomatic amylase, lipase elevations).

Dose escalation will proceed within each cohort according to the following scheme. Dose-limiting toxicity (DLT) is defined above.

The MTD is the highest dose tested in which ≤ 1 out of 6 patients has experienced a DLT.

Table 15: Dose Escalation Decision Rule Summary

Number of Patients with DLT at a Given Dose Level	Escalation Decision Rule
0 out of 3	Enter 3 patients at the next dose level.
≥2	Dose escalation will be stopped. This dose level will be declared the maximum administered dose (highest dose administered). Three (3) additional patients will be entered at the next lowest dose level if only 3 patients were treated previously at that dose.
1 out of 3	 Enter at least 3 more patients at this dose level. If 0 of these 3 patients experience DLT, proceed to the next dose level. If 1 or more of this group suffer DLT, then dose escalation is stopped, and this dose is declared the maximally administered dose. Three (3) additional patients will be entered at the next lowest dose level if only 3 patients were treated previously at that dose.
≤1 out of 6 at highest dose level below the maximum administered dose (unless ≤1 out of 6 patients have DLT's at Dose Level 2 – in which case this is also the MTD).	This is the maximum tolerated dose (MTD), and generally the recommended phase 2 dose (RP2D). At least 6 patients must be entered at the RP2D.

If ≤ 1 out of 6 patients treated at Dose Level 2 have DLT, this will be declared the maximum administered dose and the presumptive RP2D. The RP2D may be less than the MTD or the maximum administered dose, depending on toxicities in later cycles and the extent of toxicities not qualifying as DLT.

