All patients who receive a dose of pembrolizumab and trametinib will be analyzed for safety and efficacy. Subjects who discontinue from study participation prior to receiving the combination of trametinib and pembrolizumab will be replaced. Subjects in dose escalation who discontinue from study and are not evaluable for dose limiting toxicities will be replaced. Patients removed from study for unacceptable treatment related adverse event(s) will be followed until resolution or stabilization of all treatment related AEs to grade 2 or lower. However, they will not be replaced.

A group of 12 patients will be enrolled in each of the 2 expansion cohorts at the MTD. Patients will enroll into the next subsequent cohort upon completion of the previous cohort (Arm A then Arm B). A sequencing scheme will be considered as promising if at least 5 of 12 patients were to achieve a complete or partial response per RECIST 1.1. The decision rule is associated with 80% exact power with an exact alpha of 0.16 if the underlying response rate associated with a sequencing scheme were truly at least 50% compared to current expectation of 25% ORR with single agent pembrolizumab. A median PFS of 8 months in 12 patients per cohort will provide 81 power to detect a difference compared to historical PFS of about 4 months with single agent pembrolizumab with an alpha of 0.1 based on accrual time of 24 months and follow up of 12 months. A sequencing scheme will be recommended for further development based on a combination of promising efficacy (response rate, PFS) and favorable changes in the tumor immune microenvironment at rebiopsy, provided the safety and tolerability profiles are acceptable.

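### The plan contradicts itself on whether a patient whose DLT cuts treatment below 80% counts in the 3+3 rule, and the pooled 80% sets a lower combination-cycle floor in Arm A than in Arm B

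*Combined protocol and SAP*

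**What the plan says.** Section 5.4 defines a DLT-evaluable subject as one "who receives treatment for the 6 week dose-limiting toxicity (DLT) observation period and who receives at least 80% of all planned treatments". The sentence makes no exception for a patient who has a DLT. It does not say whether treatments are counted by drug, by cycle or by administration. Just before it, the same section sets a separate condition: "patients must have completed the lead in phase and also have received both trametinib and pembrolizumab concurrently to be evaluable for a DLT".

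The sentence after the definition names one group as non-evaluable and open to replacement: "A subject who does not receive at least 80% of planned treatment due to AEs that are unrelated to study treatment". Section 5.4 then allows extra enrolment to replace non-evaluable subjects, without limiting the reason. Its definition of a DLT event covers the first two cycles and carries no exposure condition.

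The Statistical Analysis Plan (Section 8.0) has two replacement sentences. The first is "Subjects in dose escalation who discontinue from study and are not evaluable for dose limiting toxicities will be replaced". The second concerns patients removed for unacceptable treatment-related adverse events, who are followed up: "However, they will not be replaced". Section 5.9, on subject replacement, is marked not applicable. Section 8.0 also bases escalation on DLTs in Cycle 2 only, where Section 5.4 uses both cycles.

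**The concern.** In a 3+3 design a single patient decides whether a level escalates, expands or stops. The text should therefore leave no doubt about who is in the denominator, above all for patients with a DLT. Here the exposure test can fail because of the DLT itself. If such a patient is set aside and another enrolled, the events that should stop escalation are the ones removed, and the error runs towards a dose that is too toxic. That dose then goes to 24 expansion patients.

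The second problem is separate. Section 5.4 says: "The goal of the dose escalation portion of the study is to assess the safety of the combination" after the lead-in. Yet the 80% is taken over both cycles together. In Arm A the lead-in consists of trametinib doses, and these can offset trametinib missed in the combination cycle. In Arm B the lead-in is one infusion and offsets almost nothing.

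**Working it through.** The plan gives no figure derived from the 80% rule, so there is none to reproduce.

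**1. Exposure floor by arm.** Inputs: trametinib on 10 days per cycle at levels 1 and 2 and on 7 days at level -1 (Table 3); one pembrolizumab infusion per cycle (Table 2); Arm A has trametinib alone in Cycle 1, Arm B pembrolizumab alone, and both arms have both drugs in Cycle 2 (Section 5.2). Assumptions: a treatment is one administration, and the lead-in was completed in full. Floor in the combination cycle = 80% of planned administrations, rounded up, minus the lead-in administrations.

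| Level | Arm | Planned over 6 weeks | 80%, rounded up | Needed in combination cycle |
|---|---|---|---|---|
| 1, 2 | A | 10 + 10 + 1 = 21 | 16.8, so 17 | 17 - 10 = 7 of 11 (64%): infusion + 6 trametinib |
| 1, 2 | B | 1 + 10 + 1 = 12 | 9.6, so 10 | 10 - 1 = 9 of 11 (82%): infusion + 8 trametinib |
| -1 | A | 7 + 7 + 1 = 15 | 12 | 12 - 7 = 5 of 8 (63%) |
| -1 | B | 1 + 7 + 1 = 9 | 7.2, so 8 | 8 - 1 = 7 of 8 (88%) |

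Counting trametinib doses only, the floors are 6 of 10 (Arm A) and 8 of 10 (Arm B) at levels 1 and 2, and 5 of 7 and 6 of 7 at level -1. The direction is the same at every level on either count.

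**2. When a DLT pushes a patient below 80% (levels 1 and 2).**

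- Arm A, stopped after 5 combination-cycle trametinib doses: 15/20 = 75%, or 16/21 = 76% with the infusion. After 6 doses: 16/20 = 80%, or 17/21 = 81%.
- Arm B, stopped after 7 doses: 7/10 = 70%, or 9/12 = 75% with both infusions. After 8 doses: 8/10 = 80%, or 10/12 = 83%.

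So a DLT that stops trametinib after 5 or fewer doses (Arm A) or 7 or fewer (Arm B) fails the test; a later one passes. Early stops are foreseeable. Section 5.2.1.2 interrupts both drugs for most Grade 3 or higher events attributed to trametinib, and Table 14 ends both for Grade 3 or 4 pneumonitis.

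**3. The sentences applied to that patient.**

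- Definition sentence (5.4): not evaluable.
- First replacement sentence (8.0), if the patient discontinues: replaced.
- Unrelated-AE sentence (5.4): does not apply, because a DLT must be judged at least possibly related.
- DLT event definition (5.4): the event is a DLT.
- Second replacement sentence (8.0), if the patient is removed for the event: not replaced.

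The first two exclude the patient and the last three point to counting the patient. If the patient were both non-evaluable and not replaced, the level would be short of the 3 or 6 the rule needs.

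**4. Size if such patients were dropped and replaced (illustration).** A level clears on 0 of 3, or on 1 of 3 followed by 0 of 3. With q = 1 - p, P(clear) = q^3 + 3pq^2 x q^3. If a fraction f of DLT patients is dropped and replaced, the DLT rate among those counted becomes p(1 - f)/(1 - pf). Both p and f are assumed.

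| True DLT rate | f = 0 | f = 0.25 | f = 0.5 |
|---|---|---|---|
| 30% | 0.49 | 0.61 | 0.76 |
| 40% | 0.31 | 0.43 | 0.60 |

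For example, p = 0.30 and f = 0.5 give 0.15/0.85 = 0.176 and P(clear) = 0.76.

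**The case against.** The strongest reply is that Section 5.4 read as a whole already counts the DLT patient. If every shortfall made a patient non-evaluable, restricting the next sentence to unrelated adverse events would do no work. The decision rules themselves count patients enrolled or treated at a level, and no sentence says to discard an observed DLT. On this reading the two replacement sentences in Section 8.0 fit together.

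Much of this stands. A reader might infer that the plan drops DLT patients; the documents do not support that. But the unrelated-AE sentence gives one reason for non-evaluability and does not amend the definition before it, and nothing states that a DLT patient is always evaluable. The favourable reading has to be inferred, patient by patient, after the toxicity is known.

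A reader might also take the probabilities above as the trial's operating characteristics. They are not: they require patients to be both dropped and replaced, in fractions the documents do not give. If such patients were excluded but not replaced, the level would be left short, which delays a decision rather than favouring escalation.

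On the asymmetry, it is fair to say that each arm escalates separately, that a sequence can be judged over the whole six weeks, and that the floor is met only by a patient with a full lead-in and the bare minimum afterwards. The documents do not show that either MTD will be wrong, nor how often patients will sit near the floor. Section 5.4 also allows extra subjects for a thorough evaluation, and the RP2D may be set below the MTD. What remains is that the minimum combination exposure differs by arm, and no reason is given.

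**Conclusion.** Two findings hold.

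First, Section 5.4 conflicts internally and with Section 8.0 on whether a patient who completed the lead-in, received both drugs and then fell below 80% because of a DLT counts in the 3+3 rule. This is a conflict of text, not a stated policy of excluding DLTs. If such patients were dropped and replaced, the bias would be towards escalation; its size depends on assumed rates and fractions.

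Second, the pooled 80% gives different combination-cycle floors: 6 of 10 trametinib doses in Arm A against 8 of 10 in Arm B at levels 1 and 2, and 5 of 8 against 7 of 8 administrations at level -1. This rests on a full lead-in and on counting administrations. The two MTDs can therefore rest on different combination exposure.

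Safety is the primary objective, and this is the denominator of its decision rule, so the text should be settled.

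**What to change.** In Section 5.4, state that a patient who completed the lead-in, received both drugs and has a DLT in the DLT window is evaluable whatever amount was received, and is not replaced. For patients without a DLT, apply the 80% threshold to the combination cycle, by drug and in the same way in both arms. That means the infusion plus at least 8 of 10 trametinib doses at levels 1 and 2, or 6 of 7 at level -1.

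Align the two replacement sentences in Section 8.0 with this, and replace the not-applicable entry in Section 5.9 with the same rule. Reconcile the DLT window (first two cycles in Section 5.4, Cycle 2 in Section 8.0). State how a DLT during the lead-in is counted, since the present requirement for a completed lead-in and concurrent dosing would leave that patient out.

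The cost is a few sentences in three sections. The one downside is that an occasional Arm A patient with low combination-cycle exposure would need replacing.

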3.0 OBJECTIVES & HYPOTHESES

3.1 Primary Objective & Hypotheses

Objective: To evaluate the safety and tolerability of pembrolizumab (MK-3475) when given in combination with trametinib in the proposed sequencing schemes in patients with advanced or metastatic non-small cell lung cancer with KRAS mutations.

Hypothesis: We hypothesize that pembrolizumab in combination with trametinib given with our lead in and intermittent sequencing schemes will be safe and tolerable.

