4.2.2 Pharmaceutical and Therapeutic Background

Trametinib is a reversible and highly selective allosteric inhibitor of mitogen-activated extracellular signal-regulated kinase (MEK1 and MEK2 activation and kinase activity). MEK proteins are critical components of the extracellular signal-regulated kinase (ERK) pathway which is commonly hyperactivated in tumor cells. Oncogenic mutations in both BRAF (a member of the RAF kinases) and RAS signal through MEK1 or MEK2.

Trametinib is administered with doses up to 2 mg once daily. Subjects should take trametinib under fasting conditions, at least 1 hour prior to or 2 hours after a meal.

Trametinib is being developed for the treatment of a variety of cancers and is currently approved in the United States, Canada, Australia, and the EU as a monotherapy treatment for the treatment of subjects with unresectable or metastatic melanoma with BRAF V600 E/K mutation (approval was also granted in Chile on 22 September 2014). It is also approved in combination with dabrafenib for the same indication in the US and Australia.

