5.2 Trial Treatments

The treatment to be used in this trial is outlined below in Table 2.

Table 2. Trial Treatments

Drug	Dose/Potency	Dose Frequency	Route of Administration	Regimen/Treatment Period	Use
Pembrolizumab (MK-3475)	200 mg	Q3W	IV infusion	Day 1 of each 3 week cycle	Experimental
Trametinib	x mg†	Daily†	PO	Daily starting D1	Experimental
† See dose escalation schema. RP2D for expansion cohorts.					

Dose Escalation Cohort (Arm A): Trametinib will be adminstered starting C1D1 and continued as per Table 3, until determination of the MTD. Pembrolizumab will be added to trametinib starting C2D1.

Dose Escalation Cohort (Arm B): Pembrolizumab will be administered starting C1D1 and trametinib will be added to pembrolizumab starting C2D1.

Expansion Cohort (Arm) A: Trametinib will be administered starting C1D1 and pembrolizumab will be added to trametinib starting C2D1 at the MTD of the combination as determined from the dose escalation portion of the study.

Expansion Cohort (Arm) B: Pembrolizumab will be administered starting C1D1 and trametinib will be added to pembrolizumab starting C2D1 at the MTD of the combination as determined from the dose escalation portion of the study.

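### The two Grade 3 or higher non-hematologic DLT criteria in Section 5.4 name different drugs, leaving a narrow gap for events known for dabrafenib (or its regimen) but for neither study drug

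*Combined protocol and SAP*

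**What the plan says.** Section 5.4 defines a DLT by a list of criteria. Every listed event must also be one "if judged by the Investigator to be possibly, probably or definitely related to study drug administration". Two of the criteria deal explicitly with clinically significant Grade 3 or higher non-hematologic toxicity:

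- The first applies when the toxicity "has not been previously identified for either pembrolizumab or dabrafenib/trametinib" and does not respond to routine supportive care.
- The second applies when the toxicity is "known to occur with either pembrolizumab or trametinib but that cannot be controlled using the recommended product-specific supportive measures".

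The list continues with a criterion for prolonged treatment interruption in Cycle 1, a set of ALT/AST thresholds, and a catch-all. The catch-all admits any other non-hematologic toxicity of Grade 2 or above that the investigator and the Sponsor Investigator judge dose limiting, with an exception for certain immune-mediated and endocrine events attributed to pembrolizumab.

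The trial treatments are pembrolizumab and trametinib. The primary objective in Section 3.1 is "To evaluate the safety and tolerability of pembrolizumab (MK-3475) when given in combination with trametinib", and Section 5.2 describes Arm A in the same terms: "Pembrolizumab will be added to trametinib starting C2D1". Arm B uses the same two drugs in the reverse order. Apart from Section 5.4 and the title of one cited reference, dabrafenib is mentioned only in the background on trametinib's approvals in Section 4.2.2: "It is also approved in combination with dabrafenib for the same indication in the US and Australia".

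**The concern.** The two criteria read as a pair, one for toxicities that are new and one for toxicities already known. A pair of that kind leaves nothing out only if new and known are judged against the same drugs. Here they are not. The first criterion drops an event because it has been seen with a drug, or a regimen, that no patient in this trial receives. The second does not pick that event up.

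What is at stake is how a severe event is classified when it is unexpected for both drugs being given. The DLT count decides escalation and the MTD, and the MTD is the dose taken into two expansion cohorts of 12 patients each. Safety and tolerability is the primary objective, so the rule that decides what counts should not depend on the profile of a third drug.

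**Working it through.** No figure in the plan depends on this wording, so there is nothing to reproduce numerically. The check sets the two criteria side by side.

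**Inputs.** Let P, T and D be the sets of toxicities known for pembrolizumab, trametinib and dabrafenib. Let R be those known for the dabrafenib/trametinib regimen. Take an event that already satisfies the other conditions: Grade 3 or higher, non-hematologic, clinically significant, not controlled by supportive measures, and at least possibly related to study drug.

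**Coverage under the two readings of the slash in Section 5.4.**

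| Reading | First criterion covers | Second criterion covers | Covered by neither |
|---|---|---|---|
| Either drug | outside P, T and D | in P or T | in D, but not in P or T |
| The two-drug regimen | outside P and R | in P or T | in R, but not in P or T |

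On the first reading, an event known only for dabrafenib fails the first criterion because it has been identified before, and fails the second because it is not known for a study drug. On the second reading, an event seen only with dabrafenib alone, and never with the regimen, does meet the first criterion. An event known for the regimen but not for trametinib alone still meets neither. The gap changes shape, but the text does not close it.

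**If both criteria named pembrolizumab and trametinib.** The first would cover everything outside P and T, and the second everything in P or T. Nothing would be left between them.

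**Other routes to a DLT in Section 5.4 for an event in the gap.**

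- ALT/AST thresholds: available, but only for liver-enzyme events.
- Interruption criterion: tied to interruption during Cycle 1 for more than 21 consecutive days. Cycle 1 is the single-agent lead-in, and the drugs are first combined at C2D1 (Section 5.2). As worded, it does not reach an interruption that begins in the combination cycle.
- Catch-all: available at Grade 2 or above, but only on a joint judgment that the event is dose limiting.

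For a non-hepatic event arising in the combination cycle, the catch-all is the only remaining route.

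**What one event can change (Table 15).** Suppose one patient's event is not counted:

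- 1 of 3 becomes 0 of 3: at dose level 1, the decision moves from adding 3 patients at the same level to opening the next level.
- 2 of 3 becomes 1 of 3: the decision moves from stopping escalation to adding 3 patients.
- 2 of 6 becomes 1 of 6: the level moves from exceeding the limit to meeting the MTD condition of at most 1 of 6.

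**The case against.** The strongest reply is that the gap is very small and largely covered. To fall into it, an event must be severe, uncontrolled and within the six-week window. It must be known for dabrafenib or its regimen, unknown for both drugs the patient is taking, and yet judged related to one of them. The documents name no such event. If the slash means the regimen, an event seen with the regimen might reasonably be regarded as known for trametinib, and the second criterion would then apply. The catch-all has a lower grade threshold and no drug list. The two explicit criteria also rest on judgment, through clinical significance and failure of supportive measures. Section 5.4 lets the RP2D be set below the MTD because of toxicities that did not qualify as DLTs, and Section 10.5 requires a meeting or call when each cohort completes DLT assessment.

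Most of this stands, and it limits the point. It does not remove it. Treating a regimen toxicity as a trametinib toxicity is an interpretation that the text does not state. The catch-all adds a further judgment, that the event is dose limiting, which the two explicit criteria do not ask for. The RP2D provision is likewise a matter of judgment.

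A reader might infer that severe new toxicities of the combination in general can escape DLT classification. The text does not support that: an uncontrolled Grade 3 or higher event that is clinically significant and not identified for any named drug meets the first criterion. A reader might also try to quantify the harm by assuming that some share of DLTs goes uncounted in the 3+3. The documents give no share and list no dabrafenib-only toxicities, so such a figure would describe undercounting in general and not this defect.

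**Conclusion.** The two drug lists are inconsistent on either reading of the slash, and the inconsistency sits in an operative rule that feeds the escalation decisions. An otherwise qualifying event known for dabrafenib or its regimen, but for neither study drug, can meet neither explicit Grade 3 or higher criterion. Unless the ALT/AST or Cycle 1 interruption criteria apply, it becomes a DLT only by discretion.

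The gap is narrow, its frequency cannot be estimated from the documents, and no effect on operating characteristics is claimed. The practical weight comes from the small counts: one reclassified event could change a dose decision.

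The conclusion assumes that the two criteria were meant to be complementary. The plan does not say so, but their new-versus-known wording points that way, and no reason is given for judging novelty against a drug outside the trial. Nothing presents the mention of dabrafenib as a deliberate choice, so it is best treated as a wording inconsistency.

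**What to change.** Reconcile the drug lists in the two Grade 3 or higher non-hematologic criteria of Section 5.4 so that both refer to the same drugs, those given in this trial. In practice this means removing the reference to dabrafenib from the first criterion. The new and known categories then leave no gap between them.

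The clinical-significance and supportive-measure conditions stay as written. The edit therefore does not make every Grade 3 or higher non-hematologic event a DLT; it only ensures that an event meeting those conditions is not lost because of which drug it was previously seen with.

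The cost is one word in Section 5.4. No dose, schedule, sample size or analysis changes.
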